11. STUDY CALENDAR

CBC w/differential (1,3)*	Х	Х	Х	Х	Х		Х		Х
Comprehensive metabolic panel (1,3,4)*	Х	Х	Х	Х	Х		Х		Х
Serum or urine pregnancy test (1, 3)	Х								Х
Urinalysis (1, 3)	Х						Х		Х
CT or MRI of chest, abdomen, pelvis (2)	Х						Х		Х
Tumor biopsy for correlative studies (5)	Х				X				
Follow-up telephone contact (6)	llow-up telephone contact (6)				Х				
*Clinical/laboratory safety assessm	ents must	be con	nple	ted w	ithin 24	4 hours	prior to	treatmen	t.

(1) Screening procedures must be completed within 21 days of initiating study treatment, with the exception of the serum or urine pregnancy test, which must be completed within 7 days of initiating study treatment. Protocol-specified screening procedures that are performed as part of standard of care and are within the specified timeframes may be used for screening purposes.

(2) Baseline imaging can include either (a) CT, spiral CT or MRI, or (b) FDG-PET with diagnostic CT performed with IV and oral contrast and CT acquired with 5 mm or less slice thickness. Imaging studies used for baseline tumor measurements must be performed within 21 days of initiating study treatment. Imaging studies are performed every 2 cycles (6 weeks, 42 days) for the first 36 weeks of study treatment, and then every 3 cycles (9 weeks, 63 days) thereafter. Imaging studies may be performed +/- 5 days from the required date. In the event of dose delays/holds, imaging studies should still be obtained at the scheduled timepoints as measured from cycle 1 day 1, without delays to account for dose delays/holds. Confirmatory scans must be obtained at least 4 weeks after the documentation of an objective response. It is acceptable to perform confirmatory assessments at the next appointed evaluation per protocol. Response assessment should include assessment of all sites of disease and use the same imaging method as used at baseline whenever possible.

(3) All laboratory studies may be performed +/- 3 days from the required date. Local laboratory testing is permitted, except for the serum/urine pregnancy test.

(4) Comprehensive metabolic panel includes albumin, alkaline phosphatase, total bilirubin, bicarbonate, blood urea nitrogen, calcium, chloride, creatinine, glucose, potassium, total protein, AST, ALT and sodium.

(5) The first 10 patients enrolled on the study will undergo paired pre-treatment and on-treatment biopsies. The baseline biopsy specimen must be obtained within 21 days of cycle 1 day 1, provided consent is obtained and other eligibility criteria are met. The on-treatment biopsy specimen will be performed cycle 2, days 1 or 2. Biopsies will be obtained from the same anatomic site of disease whenever possible.

(6) A post-study follow-up contact via telephone by research staff will be conducted every 3 months during the first year after the end of study participation, and then every 6 months thereafter. Information is obtained on disease status, survival status, and new anti-cancer therapy received. Follow-up continues for at least 3 years as measured from the date of study registration or until death, whichever comes first.

(7) The end-of-study visit must be scheduled within 28 days after the last dose of study drug (+/-7 days) and before starting any new anti-neoplastic therapy.

(8) Clinical assessments will occur on days 1, 8 and 15 of cycle 1, and then on day 1 of all cycles thereafter. Clinical assessments may occur +/- 3 days from the planned date but must occur within 24 hours of ATX-101 administration.

12. MEASUREMENT OF EFFECT

12.1 Antitumor Effect – Solid Tumors

For the purposes of this study, patients will be re-evaluated for response every 6 weeks. In addition to a baseline scan, confirmatory scans should also be obtained 4 weeks following initial documentation of objective response.

Response and progression will be evaluated in this study using the new international criteria proposed by the revised Response Evaluation Criteria in Solid Tumors (RECIST) guideline (version 1.1). Changes in the largest diameter (unidimensional measurement) of the tumor lesions and the shortest diameter in the case of malignant lymph nodes are used in the RECIST criteria.

12.1.1 Definitions

Evaluable for toxicity: All patients will be evaluable for toxicity from the time of their first treatment with ATX-101. The safety population will consist of all patients who received at least one dose of study drug.

Evaluable for objective response: Only those patients who have measurable disease present at baseline, have received at least one cycle of therapy, and have had their disease re-evaluated will be considered evaluable for response. These patients will have their response classified according to the definitions stated below. (Note: Patients who exhibit objective disease progression prior to the end of cycle 1 will also be considered evaluable.) Patients who end study treatment during cycle one of treatment may be replaced.

Evaluable Non-Target Disease Response: Patients who have lesions present at baseline that are evaluable but do not meet the definitions of measurable disease, have received at least one cycle of therapy, and have had their disease re-evaluated will be considered evaluable for non-target disease. The response assessment is based on the presence, absence, or unequivocal progression of the lesions.

12.2 Disease Parameters

Measurable disease: Measurable lesions are defined as those that can be accurately measured in at least one dimension (longest diameter to be recorded for non-nodal lesions and short axis for nodal lesions) as ≥ 20 mm by chest x-ray, as ≥ 10 mm with CT scan, or ≥ 10 mm with calipers

by clinical exam. All tumor measurements must be recorded in millimeters (or decimal fractions of centimeters).

Note: Tumor lesions that are situated in a previously irradiated area might or might not be considered measurable. If the investigator thinks it appropriate to include them, the conditions under which such lesions should be considered must be defined in the protocol.

Malignant lymph nodes: To be considered pathologically enlarged and measurable, a lymph node must be ≥ 15 mm in short axis when assessed by CT scan (CT scan slice thickness recommended to be no greater than 5 mm). At baseline and in follow-up, only the short axis will be measured and followed.

Non-measurable disease: All other lesions (or sites of disease), including small lesions (longest diameter < 10 mm or pathological lymph nodes with \geq 10 to < 15 mm short axis), are considered non-measurable disease. Bone lesions, leptomeningeal disease, ascites, pleural/pericardial effusions, lymphangitis cutis/pneumonitis, inflammatory breast disease, and abdominal masses (not followed by CT or MRI), are considered as non-measurable.

Note: Cystic lesions that meet the criteria for radiographically defined simple cysts should not be considered as malignant lesions (neither measurable nor non-measurable) since they are, by definition, simple cysts. Cystic lesions thought to represent cystic metastases can be considered as measurable lesions, if they meet the definition of measurability described above. However, if non-cystic lesions are present in the same patient, these are preferred for selection as target lesions.

Target lesions: All measurable lesions up to a maximum of 2 lesions per organ and 5 lesions in total, representative of all involved organs, should be identified as target lesions and recorded and measured at baseline. Target lesions should be selected on the basis of their size (lesions with the longest diameter), be representative of all involved organs, but in addition should be those that lend themselves to reproducible repeated measurements. It may be the case that, on occasion, the largest lesion does not lend itself to reproducible measurement in which circumstance the next largest lesion which can be measured reproducibly should be selected. A sum of the diameters (longest for non-nodal lesions, short axis for nodal lesions) for all target lesions will be calculated and reported as the baseline sum diameters. If lymph nodes are to be included in the sum, then only the short axis is added into the sum. The baseline sum diameters will be used as reference to further characterize any objective tumor regression in the measurable dimension of the disease.

Non-target lesions: All other lesions (or sites of disease) including any measurable lesions over and above the 5 target lesions should be identified as non-target lesions and should also be recorded at baseline. Measurements of these lesions are not required, but the presence, absence, or in rare cases unequivocal progression of each should be noted throughout follow-up.

12.3 Methods for Evaluation of Measurable Disease

All measurements should be taken and recorded in metric notation using a ruler or calipers. All baseline evaluations should be performed as closely as possible to the beginning of treatment and never more than 4 weeks before the beginning of the treatment.

The same method of assessment and the same technique should be used to characterize each identified and reported lesion at baseline and during follow-up. Imaging-based evaluation is preferred to evaluation by clinical examination unless the lesion(s) being followed cannot be imaged but are assessable by clinical exam.

Clinical lesions: Clinical lesions will only be considered measurable when they are superficial (e.g., skin nodules and palpable lymph nodes) and ≥ 10 mm diameter as assessed using calipers (e.g., skin nodules). In the case of skin lesions, documentation by color photography, including a ruler to estimate the size of the lesion, is recommended.

Chest x-ray: Lesions on chest x-ray are acceptable as measurable lesions when they are clearly defined and surrounded by aerated lung. However, CT is preferable.

Conventional CT and MRI: This guideline has defined measurability of lesions on CT scan based on the assumption that CT slice thickness is 5 mm or less. If CT scans have slice thickness greater than 5 mm, the minimum size for a measurable lesion should be twice the slice thickness. MRI is also acceptable in certain situations (e.g., for body scans).

Use of MRI remains a complex issue. MRI has excellent contrast, spatial, and temporal resolution; however, there are many image acquisition variables involved in MRI, which greatly impact image quality, lesion conspicuity, and measurement. Furthermore, the availability of MRI is variable globally. As with CT, if an MRI is performed, the technical specifications of the scanning sequences used should be optimized for the evaluation of the type and site of disease. Furthermore, as with CT, the modality used at follow-up should be the same as was used at baseline and the lesions should be measured/assessed on the same pulse sequence. It is beyond the scope of the RECIST guidelines to prescribe specific MRI pulse sequence parameters for all scanners, body parts, and diseases. Ideally, the same type of scanner should be used and the image acquisition protocol should be followed as closely as possible to prior scans. Body scans should be performed with breath-hold scanning techniques, if possible.

PET-CT: At present, the low dose or attenuation correction CT portion of a combined PET-CT is not always of optimal diagnostic CT quality for use with RECIST measurements. However, if the site can document that the CT performed as part of a PET-CT is of identical diagnostic quality to a diagnostic CT (with IV and oral contrast), then the CT portion of the PET-CT can be used for RECIST measurements and can be used interchangeably with conventional CT in accurately measuring cancer lesions over time. Note, however, that the PET portion of the CT introduces additional data which may bias an investigator if it is not routinely or serially performed.

Ultrasound: Ultrasound is not useful in assessment of lesion size and should not be used as a method of measurement. Ultrasound examinations cannot be reproduced in their entirety for independent review at a later date and, because they are operator dependent, it cannot be

guaranteed that the same technique and measurements will be taken from one assessment to the next. If new lesions are identified by ultrasound in the course of the study, confirmation by CT or MRI is advised. If there is concern about radiation exposure at CT, MRI may be used instead of CT in selected instances.

Endoscopy/Laparoscopy: The utilization of these techniques for objective tumor evaluation is not advised. However, such techniques may be useful to confirm complete pathological response when biopsies are obtained or to determine relapse in trials where recurrence following complete response (CR) or surgical resection is an endpoint.

Tumor markers: Tumor markers will not be used in this study.

Cytology/Histology: These techniques can be used to differentiate between partial responses (PR) and complete responses (CR) in rare cases (e.g., residual lesions in tumor types, such as germ cell tumors, where known residual benign tumors can remain).

The cytological confirmation of the neoplastic origin of any effusion that appears or worsens during treatment when the measurable tumor has met criteria for response or stable disease is mandatory to differentiate between response or stable disease (an effusion may be a side effect of the treatment) and progressive disease.

FDG-PET: While FDG-PET response assessments need additional study, it is sometimes reasonable to incorporate the use of FDG-PET scanning to complement CT scanning in assessment of progression (particularly possible 'new' disease). New lesions on the basis of FDG-PET imaging can be identified according to the following algorithm:

- Negative FDG-PET at baseline, with a positive FDG-PET at follow-up is a sign of PD based on a new lesion.
- No FDG-PET at baseline and a positive FDG-PET at follow-up: If the positive FDG-PET at follow-up corresponds to a new site of disease confirmed by CT, this is PD. If the positive FDG-PET at follow-up is not confirmed as a new site of disease on CT, additional follow-up CT scans are needed to determine if there is truly progression occurring at that site (if so, the date of PD will be the date of the initial abnormal FDG-PET scan). If the positive FDG-PET at follow-up corresponds to a pre-existing site of disease on CT that is not progressing on the basis of the anatomic images, this is not PD.
- FDG-PET may be used to upgrade a response to a CR in a manner similar to a biopsy in cases where a residual radiographic abnormality is thought to represent fibrosis or scarring. The use of FDG-PET in this circumstance should be prospectively described in the protocol and supported by disease-specific medical literature for the indication. However, it must be acknowledged that both approaches may lead to false positive CR due to limitations of FDG-PET and biopsy resolution/sensitivity.

Note: A 'positive' FDG-PET scan lesion means one which is FDG avid with an uptake greater than twice that of the surrounding tissue on the attenuation corrected image.

12.4 Response Criteria

12.4.1 Evaluation of Target Lesions

Complete Response (CR): Disappearance of all target lesions. Any pathological lymph nodes (whether target or non-target) must have reduction in short axis to < 10 mm.

Partial Response (PR): At least a 30% decrease in the sum of the diameters of target lesions, taking as reference the baseline sum diameters.

Progressive Disease (PD): At least a 20% increase in the sum of the diameters of target lesions, taking as reference the smallest sum on study (this includes the baseline sum if that is the smallest on study). In addition to the relative increase of 20%, the sum must also demonstrate an absolute increase of at least 5 mm. (Note: the appearance of one or more new lesions is also considered progressions).

Stable Disease (SD): Neither sufficient shrinkage to qualify for PR nor sufficient increase to qualify for PD, taking as reference the smallest sum diameters while on study.

12.4.2 Evaluation of Non-Target Lesions

Complete Response (CR): Disappearance of all non-target lesions and normalization of tumor marker level. All lymph nodes must be non-pathological in size (<10 mm short axis).

Note: If tumor markers are initially above the upper normal limit, they must normalize for a patient to be considered in complete clinical response.

Non-CR/Non-PD: Persistence of one or more non-target lesion(s) and/or maintenance of tumor marker level above the normal limits.

Progressive Disease (PD): Appearance of one or more new lesions and/or unequivocal progression of existing non-target lesions. Unequivocal progression should not normally trump target lesion status. It must be representative of overall disease status change, not a single lesion increase. Although a clear progression of "non-target" lesions only is exceptional, the opinion of the treating physician should prevail in such circumstances, and the progression status should be confirmed at a later time by the review panel (or Principal Investigator).

12.4.3 Evaluation of Best Overall Response

The best overall response is the best response recorded from the start of the treatment until disease progression/recurrence (taking as reference for progressive disease the smallest measurements recorded since the treatment started). The patient's best response assignment will depend on the achievement of both measurement and confirmation criteria.

Target Lesions	Non-Target Lesions	New Lesions	Overall Response	Best Overall Response when Confirmation is Required*
CR	CR	No	CR	≥4 wks. Confirmation**
CR	Non-CR/Non-PD	No	PR	
CR	Not evaluated	No	PR	≥ 4 wks.
PR	Non-CR/Non-PD/not evaluated	No	PR	Confirmation**
SD	Non-CR/Non-PD/not evaluated	No	SD	documented at least once ≥4 wks. from baseline**
PD	Any	Yes or No	PD	
Any	PD***	Yes or No	PD	no prior SD, PR or CR
Any	Any	Yes	PD	

* See RECIST 1.1 manuscript for further details on what is evidence of a new lesion.

** Only for non-randomized trials with response as primary endpoint.

*** In exceptional circumstances, unequivocal progression in non-target lesions may be accepted as disease progression.

Note: Patients with a global deterioration of health status requiring discontinuation of treatment without objective evidence of disease progression at that time should be reported as "symptomatic deterioration." Every effort should be made to document the objective progression even after discontinuation of treatment.

12.5 Duration of Response

Duration of overall response: The duration of overall response is measured from the time measurement criteria are met for CR or PR (whichever is first recorded) until the first date that recurrent or progressive disease is objectively documented (taking as reference for progressive disease the smallest measurements recorded since the treatment started).

The duration of overall CR is measured from the time measurement criteria are first met for CR until the first date that progressive disease is objectively documented.

Duration of stable disease: Stable disease is measured from the start of the treatment until the criteria for progression are met, taking as reference the smallest measurements recorded since the treatment started, including the baseline measurements.

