2.2 Secondary Objectives

- 2.2.1 To perform a safety lead-in among the first 10 patients enrolled and treated on the study to confirm the safety and tolerability of the drug in sarcoma patients.
- 2.2.2 To further evaluate the safety profile of ATX-101 by assessing adverse event rates (according to National Cancer Institute CTCAE version 4.0 criteria) in patients treated with this agent.
- 2.2.3 To assess the efficacy of ATX-101 in patients with advanced LMS and dedifferentiated LPS by evaluating the objective response rate (according to RECIST 1.1 criteria), duration of response, median progression free survival and median overall survival.

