12.6 Progression-Free Survival

Progression free survival is defined as the duration of time from start of treatment to time of progression or death, whichever occurs first.

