15.4 Analysis of Secondary Endpoints

Safety Lead-In: A safety lead-in will be conducted as described in Section 4.2. A summary of the adverse events and any DLT observed during the safety lead-in phase will be provided, as well as the study team's assessment of whether the protocol-specified dose and schedule is tolerable.

Adverse event rates: Adverse events will be recorded at each clinical visit and will be categorized according to NCI CTCAE version 4.0. Adverse event rates will be reported as counts and percentages per adverse event basis by grade.

Overall survival and progression free survival: Overall survival is defined as the time from the date of first treatment with study drug to the time of death from any cause or last follow-up if alive. Progression free survival is defined as the time from first treatment with the study drug to the earliest of either disease progression or death from any cause. Patients who are alive and progression free will be censored at the time of their last follow-up. The Kaplan-Meir method

will be used to evaluate all time to event endpoints. Median overall survival and median progression free survival will be reported with 95% confidence intervals.

Response rate: Patient responses will be evaluated according to RECIST version 1.1 as described in section 12. The response rate is defined as the number of patients having a best objective tumor status of complete response or partial response lasting at least four weeks divided by the number of evaluable patients. The response rate will be reported with 95% confidence intervals.

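### Duration of response does not count death as an end event and has no censoring rule, so the estimate can run long if a responder dies without documented progression

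*Combined protocol and SAP*

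**What the plan says.** Section 2.2 (item 2.2.3) lists duration of response among the efficacy measures of the secondary objectives: "objective response rate (according to RECIST 1.1 criteria), duration of response, median progression free survival and median overall survival".

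Section 12.5 starts the clock when CR or PR criteria are first met and runs it "until the first date that recurrent or progressive disease is objectively documented". Duration of CR runs "until the first date that progressive disease is objectively documented". Death appears in neither sentence.

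The next section, 12.6, ends progression-free survival (PFS) at "time of progression or death, whichever occurs first". Section 15.4 says the same in other words: the "earliest of either disease progression or death from any cause".

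Section 15.4 has no paragraph on duration of response. In the paragraph on overall survival and PFS it says that the Kaplan-Meier method "will be used to evaluate all time to event endpoints". The only censoring rule for a progression endpoint is in that paragraph: "Patients who are alive and progression free will be censored at the time of their last follow-up".

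**The concern.** Both PFS definitions name death and both response durations omit it, so the two kinds of endpoint differ on the face of the text. A responder who dies with no documented progression has a PFS event but no end event for duration of response. Under Kaplan-Meier, a patient without the defined end event is normally censored. Censoring treats the dead patient as someone who could still have remained in response, and so tends to make responses look longer lasting than they were.

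The plan does not settle the matter elsewhere, so the analyst would have to choose a rule, possibly after seeing the data. At stake is a descriptive estimate in a small subgroup, not the trial's go/no-go decision.

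**Working it through.** **The plan's own figures.** The documents state no number for duration of response. The only stated calculation is the two-stage design in 15.1: continue with at least 4 of 10, promising with at least 15 of 34, 30% versus 55%, one-sided alpha 0.05, power 85%. The exact probability that X1 ≥ 4 (of 10) and X1 + X2 ≥ 15 (of 34) is 0.0456 at 30% and 0.853 at 55%, so the design reproduces. Duration of response does not enter it.

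**Can such a death occur here?** Section 7.3 lets treatment stop for clinical progression judged by the investigator. The note in 12.4.3 foresees deterioration without objective progression; it asks for efforts to document progression later but sets no scan schedule. The imaging intervals in the section 11 calendar are tied to weeks and cycles of study treatment. Section 7.4 follows patients who stopped for progression for survival only. So a responder can decline clinically, stop treatment and die, with the death recorded but no objective progression.

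**What the text does with that patient.**

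| Endpoint | End event met? | Censoring rule that applies? |
|---|---|---|
| PFS (12.6, 15.4) | Yes, death | Not needed |
| Duration of response (12.5) | No | None; the 15.4 rule covers only patients who are alive |
| Duration of CR (12.5) | No | None |

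**Direction.** With n responders at risk at the time of death, counting the death multiplies the Kaplan-Meier curve by (1 − 1/n); censoring it there multiplies by 1. The later risk sets are the same. The curve with the death censored is therefore never below the curve with it counted. This is exact for censoring at the date of death. If censoring were moved back to the last scan, the curve could sit slightly lower between that scan and the death.

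**Size, under an assumption.** Let progression and death without documented progression have constant hazards λp and λd, and let f = λd/(λp + λd) be the share of first events that are such deaths.

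- Median with death counted: ln 2/(λp + λd)
- Median with death censored: ln 2/λp
- Ratio: (λp + λd)/λp = 1/(1 − f)

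The documents give neither f nor a median. The illustration takes a median of 6.0 months to progression or death.

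| Assumed f | 1/(1 − f) | Median if deaths censored (months) |
|---|---|---|
| 5% | 1.05 | 6.3 |
| 10% | 1.11 | 6.7 |
| 20% | 1.25 | 7.5 |
| 30% | 1.43 | 8.6 |

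**How many patients.** Section 3.2 reports no RECIST responses among 21 phase 1 patients. At assumed response rates of 5%, 10%, 15% and 20%, the expected number of responders is 34 × rate = 1.7, 3.4, 5.1 and 6.8. At 20% response and f = 20%, 6.8 × 0.20 ≈ 1.4 responders would be affected.

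**What one death can do.** Take five invented durations: 2, 3, 5, 8 and 12 months, all events. The curve falls to 0.8, 0.6 and 0.4, so the median is 5. Now treat one of the five as a censored death:

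- At month 3: 0.8, then 0.8 × 2/3 = 0.53 at month 5, then 0.53 × 1/2 = 0.27 at month 8. The median is 8.
- At month 5: 0.8, 0.6, then 0.6 × 1/2 = 0.3 at month 8. The median is 8.
- At month 2, 8 or 12: the median stays at 5.

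**The case against.** A reader might infer that the plan prescribes censoring these deaths and that the reported duration is therefore overstated. The documents do not support that. No section says such a death is censored, and the one related rule is limited to patients who are alive. The death could be censored at its date, censored at the last scan, or counted as an event. Censoring is the natural result of applying 12.5 literally, but it remains an inference, and any overstatement also requires that such a death occurs.

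Four further points can be made.

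- The analysis itself is barely specified. Section 4.1 omits duration of response from its list of secondary endpoints, and 15.4 promises medians only for overall survival and PFS. Kaplan-Meier for duration of response is a fair reading of the general sentence, no more. This stands, and is a reason to add a line to 15.4.
- Time to documented progression among responders is a legitimate quantity. It is too long only relative to time to progression or death. This stands, so the bias is stated against that target; nothing in the plan explains why the two durations should treat death differently from PFS.
- Scans every 6 weeks to week 36 and every 9 weeks thereafter, disease-status follow-up of patients who have not progressed, and the request to document progression after deterioration should make such deaths uncommon. This stands as a limit on size. It does not close the gap for a patient who stops for clinical decline.
- Percentages from a smooth hazard model say little about two to seven patients. This also stands: they show scale and are not a forecast.

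**Conclusion.** The point holds, and it is minor. Section 12.5 omits death from the end of both response durations, PFS counts it, and 15.4 supplies no censoring rule that covers a responder who has died. If such a death is censored at its date, the estimated duration is lengthened or left unchanged relative to time to progression or death, never shortened.

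The amount cannot be fixed from the documents. The 11%, 25% and 43% figures rest on assumed death shares of 10%, 20% and 30% and on constant hazards. The expected responder counts rest on assumed response rates. With so few responders, a single death may shift the median appreciably or not at all.

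The effect is confined to a descriptive secondary measure. The 12-week progression-free rate already requires patients to be alive, so the stage 1 rule, the final rule, alpha and power do not change.

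**What to change.** In 12.5, define duration of overall response as the time from first CR or PR, and duration of CR as the time from first CR, to the earlier of documented progression or death from any cause.

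In 15.4, add a line on duration of response stating that it is estimated by Kaplan-Meier among responders, and that responders alive and progression free are censored by the same rule as PFS. That rule is currently last follow-up. If the sponsor prefers the last tumour assessment, both endpoints should change together; changing only one would create a new mismatch.

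The cost is a clause in each definition and one added line. Sample size, alpha, power and data collection are unaffected. The one downside is that the reported duration may be slightly shorter.
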